2.3 Secondary Objectives

The secondary objectives of this study are to:

- Estimate the progression-free survival (PFS) at 6 months for patients with ER(-)/PR(-)/AR(+) metastatic breast cancer
- Evaluate the safety of bicalutamide for patients with ER(-)/PR(-)/AR(+) metastatic breast cancer.
- Perform correlative studies including:
 - Monitoring of changes in estradiol, total and free testosterone and sex-hormone binding globulin in response to androgen blockade in women with breast cancer
 - Immunohistochemical analysis of tissue including cytokeratins 5/6 and 17, SPDEF, ALCAM, ERBB2, FGFR4 and PSA
 - Collection and storage of AR+ paraffin embedded tissue samples from primary or metastatic site, if available. These samples will be used to further investigate the biology of AR+ breast cancer (ie, by building a tissue microarray).

3.1 BACKGROUND AND RATIONALE

Breast cancer remains one of the most common diseases affecting women with a lifetime risk of approximately 13% (or 1 in 7 women)². It is estimated that in 2008 over 180,000 women will develop breast cancer and ~40,400 will die of their disease³. Approximately 70% of patients with breast cancer have tumors that express estrogen receptors or progesterone receptors, or both, and are candidates for hormonal therapy.

Estrogen receptor-negative, progesterone receptor-negative (ER(-)/PR(-)) breast cancer represents approximately 25 to 30% of all breast cancers and generally has a more aggressive clinical course than hormone receptor-positive disease. Therapeutic options for these patients are limited. Patients with ER(-)/PR(-) tumors gain little or no benefit from anti-estrogen therapy and targeted therapy is limited to trastuzumab in those patients with tumors that overexpress Her2/neu.

In addition to ER and PR, breast cancer cells express other nuclear hormone receptors. The androgen receptor (AR) is expressed in 60 to 80% of breast cancers and implicated in breast cancer biology⁴. Among postmenopausal women, high androgen levels are associated with an increased risk of developing breast cancer⁵. Furthermore, androgens can induce proliferation in breast tissue, and initiate tumor formation via the AR in animal models⁶.

A recent analyses of gene expression profiles of primary breast cancers from investigators at MSKCC identified a subset of ER(-)/PR(-) tumors with a molecular signature that suggests an active hormonally regulated transcriptional program¹. Gene expression signatures were used to develop a predictive model that can identify molecularly similar breast cancers in an independent human breast cancer data set and among breast cancer cell lines. A cell line with this signature demonstrated a proliferative response to androgen in an androgen receptor dependent manner that was inhibited by anti-androgens. This subset of breast cancers (ER(-) Class A) characterized by a hormonally related transcriptional program and proliferative response to androgen, suggests the potential for therapeutic strategies targeting the androgen signaling pathway. This trial is designed to test this hypothesis.

Admittedly, the mechanisms by which androgens contribute to increased risk of breast cancer are not well understood. In an older literature, androgens appeared to have a growth inhibitory effect in animal and cell-line experiments. However, this idea has not been supported in studies of human populations. Recent studies of CAG-repeat length in androgen receptor polymorphisms suggest that differing AR polymorphisms may modulate a woman's risk of breast cancer. It has been postulated that an association exists between AR CAG-repeat length and BRCA1-related breast cancer risk. Androgens may have both direct and indirect effects on breast tissue and ultimately breast cancer risk. As the mechanism by which androgens influence breast cancer risk remain unclear, we have designed this trial to test the hypothesis derived from our preclinical work that targeting androgen receptor signaling in the subset of ER(-) Class A tumors will be of benefit.

IRB#: 07-022A(13)

3.2 Studies of Bicalutamide in men with prostate cancer

Bicalutamide is an orally active, nonsteroidal anti-androgen that competitively inhibits the action of androgens by binding to cytosol androgen receptors in target tissues. Studies have demonstrated tolerability and efficacy of bicalutamide in men with locally advanced and metastatic prostate cancer.

Bicalutamide was initially evaluated in patients with prostate cancer at the 50 mg per day dose for use in combination with castration in combined androgen blockage (CAB) therapy. CAB therapy consists of an antiandrogen with either surgical castration or medical castration with a luteinizing hormone-releasing hormone analogue (LHRH-A).

Subsequently, studies evaluated bicalutamide at a dose of 50 mg per day (licensed for use in CAB) as monotherapy in patients with previously untreated, advanced prostate cancer. After bicalutamide 50 mg per day was shown to be inferior to castration in terms of survival, dose-finding phase II studies were performed to evaluate whether higher doses of bicalutamide would be more effective. Pharmacodynamic studies showed an increasing prostate specific antigen (PSA) response with increasing dose that reached a plateau at 150 - 200 mg per day, with the PSA response seen with 150 mg per day similar to that seen with castration. The use of bicalutamide in doses higher than 150 mg per day was not limited by safety concerns, as doses of up to 600 mg per day did not cause dose-related increases in adverse events⁷.

A dose of bicalutamide 150 mg per day was selected for development as monotherapy based on pharmacodynamic results that showed the PSA response after 3 months of treatment at this dose level (>92% reduction) was comparable to that seen in patients who had undergone surgical castration. Bicalutamide 150 mg per day was subsequently evaluated against castration in two large randomized Phase III studies in men with M0 or M1 disease. Bicalutamide 150 mg per day demonstrated good tolerability in these studies⁸. 6% of bicalutamide-treated patients withdrew from treatment due to an adverse event. The reported side effect profile included gynecomastia and breast pain (35 - 40%), hot flashes (6-13%) and diarrhea (4-5%).

The corresponding pharmacokinetic data for the relationship between (*R*)-bicalutamide (the active enantiomer) steady-state concentration (Css) and dosage shows a departure in linearity at doses >50 mg/day and a clear plateau for doses > 300mg/day⁹. Pharmacokinetics are unaffected by age, body-weight, renal impairment and mild-to-moderate hepatic impairment. Bicalutamide does not demonstrate any clinically relevant interaction with other drugs.

A dose of bicalutamide 150 mg/day was selected for the ongoing bicalutamide ('Casodex') Early Prostate Cancer (EPC) Program. This program was designed to evaluate whether the addition of bicalutamide 150 mg to standard care can reduce the risk of disease progression, as well as improve overall survival in patients with localized or locally advanced prostate cancer. Consisting of three randomized, double-blind, placebo-controlled trials, it is the largest prostate cancer study to date. Following standard care, 8113 men with localized or locally advanced prostate cancer were randomized to receive oral bicalutamide 150 mg once daily or oral placebo. At a median follow-up of 7.4 years, the data suggest that adjuvant hormonal therapy for patients

IRB#: 07-022A(13)

at low risk of disease progression (ie localized disease) is currently not appropriate. For patients with locally advanced disease, however, the addition of bicalutamide to standard care significantly increases PFS and shows a trend towards improved OS¹⁰.

For safety and tolerability, the most common adverse events reported with bicalutamide were breast pain (73.6%) and gynecomastia (68.8%). Symptoms were reported as mild to moderate in over 90% of cases. Symptoms typically developed within the first 6 to 9 months of treatment. Other adverse events were infrequent and included impotence (9.3% with bicalutamide and 6.5% with standard care alone), decreased libido (3.6% and 1.2%, respectively), hotflushes (9.2% and 5.4% respectively), and abnormal liver function tests (3.1% and 1.7%, respectively). Withdrawal rates from the study due to adverse events were 29.3% with bicalutamide and 10.0% with standard care alone. Withdrawal rates secondary to breast pain and/or gynecomastia were 16.8% and 0.7% respectively. In the bicalutamide group, fewer patients died from prostate cancer than those receiving standard care alone (6.4% vs 7.5%). Deaths from heart failure and gastrointestinal carcinoma were higher in the bicalutamide group, though there were no consistent patterns to suggest that these were due to drug toxicity.

IRB#: 07-022A(13)

[figure not shown]
10

The most common adverse events and causes of death, as number (%) of patients ¹⁰					
Variable	Bicalutamide 150 mg + Standard care alone				
	standard care				
	N=4022	N=4031			
Adverse Event					
Breast pain	2962 (73.6%)	308 (7.6%)			
Gynecomastia	2766 (68.8%)	334 (8.3%)			
Pharyngitis	448 (11.1%)	470 (11.7%)			
Asthenia	442 (11.0%)	315 (7.8%)			
Back pain	420 (10.4%)	490 (12.2%)			
Rash	404 (10.0%)	337 (8.4%)			
Constipation	380 (9.4%)	314 (7.8%)			
Impotence	375 (9.3%)	263 (6.5%)			
Hot flushes	370 (9.2%)	216 (5.4%)			
Arthralgia	355 (8.8%)	405 (10.0%)			
Cause of death					
Prostate cancer	257 (6.4%)	302 (7.5%)			
Myocardial infarction	81 (2.0%)	76 (1.9%)			
Cause unknown	68 (1.7%)	63 (1.6%)			
Gastrointestinal carcinoma	54 (1.3%)	38 (0.9%)			
Heart failure	49 (1.2%)	25 (0.6%)			
Cerebrovascular accident	47 (1.2%)	45 (1.1%)			
Lung carcinoma	44 (1.1%)	47 (1.2%)			
Heart arrest	37 (0.9%)	33 (0.8%)			
Pneumonia	34 (0.8%)	45 (1.1%)			

The most common side effects of gynecomastia and breast pain reflect the pharmacology of bicalutamide. Gynecomastia, the proliferation of the glandular component of the male breast, occurs because of an increase in the ratio of estrogen to androgen. Bicalutamide treatment causes gynecomastia because of blockade of androgenic activity and the increase in peripheral aromatization of androgens to estrogens. The reported rates of gynecomastia and breast pain were lower in trials of bicalutamide in metastatic patients than in the EPC study of patients with localized or locally advanced disease. The toxicity profile of bicalutamide 50 mg in combination with an LHRH analogue (as included in the AstraZeneca package insert) is included in Appendix A.

3.3 Studies of Bicalutamide in Women

In two small studies bicalutamide has been given at a dose of 25 mg per day to women with polycystic ovary disease and for treatment of hirsuitism^{11,12}. To date, there have been no studies of bicalutamide as an anti-cancer therapy in women, or using doses above 25 mg per day.

IRB#: 07-022A(13)

3.4 Rationale for bicalutamide study dose selection

Though bicalutamide has not been well tested in women, the extensive studies of this drug in men with prostate cancer demonstrating good tolerability provide support for its use in women. The selection of a dose of 150 mg per day is based on pharmacokinetic, pharmacodynamic and safety data from studies performed in men with prostate cancer. Notably, studies of doses above 150 mg (up to 600 mg) failed to show dose-limiting toxicity. The dose of 150 mg reflects an optimal steady-state concentration and PSA-lowering effect in men with prostate cancer.

Because there may be differences seen with the use of bicalutamide in women, this study has been designed with a dose reduction schema for toxicity. Correlative studies include a panel of serum hormonal studies that will provide information on differences seen in the hormonal/metabolic pathways in women. The goal of this study is to test the hypothesis that androgen blockade in women with ER(-)/PR(-)/AR(+) breast cancer (ER(-) Class A) is an effective hormonal treatment. This study will not perform pharmacokinetic and pharmacodynamic studies.

4.1 OVERVIEW OF STUDY DESIGN/INTERVENTION

4.2 Design

This is a multicenter, open-label, one-stage, phase II study to evaluate the antitumor activity and safety of bicalutamide administered orally daily to patients with ER(-)/PR(-)/AR(+) metastatic breast cancer. Patients with non-measurable or measurable, metastatic breast cancer are eligible. Prior neo-adjuvant or adjuvant chemotherapy is permitted. Prior therapy with trastuzumab is necessary for patients with Her-2/neu positive disease (3+ IHC or FISH > 2.0). There is no limitation on prior treatment with chemotherapy or hormonal therapies.

After signing the protocol consent form for androgen receptor testing, the patient's tumor will be evaluated for androgen receptor status using a commercially available immunohistochemical analysis. Androgen receptor testing may occur on primary breast tumor or tissue from biopsy of a metastatic site. Participating centers may send unstained slides to MSKCC for ER, PR and AR testing. Participating sites may instead choose to perform androgen receptor testing themselves however, estrogen receptor, progesterone receptor and androgen receptor status will be centrally confirmed at Memorial Sloan-Kettering Cancer Center by the Department of Pathology for tumors which test ER(-)/PR(-)/AR(+) locally. If this patient meets the remaining eligibility criteria for study participation, they may later consent to treatment on study. Patients with ER(-)/PR(-)/AR(+) breast cancer on local testing may begin bicalutamide if otherwise eligible while confirmation of receptor status at MSKCC takes place. If the patient's tumor is AR(-) at MSKCC, or if either estrogen or progesterone receptors are positive at MSKCC, the patient may continue on treatment with bicalutamide if the tumor tested ER(-), PR(-), AR(+) locally.

IRB#: 07-022A(13)

The primary aim of the study is to evaluate the efficacy of bicalutamide in terms of response (CR+PR) and SD at 6 months. The study has a projected enrollment of 28 patients. If 4 or more patients demonstrate a response (defined as a CR, PR or SD by RECIST criteria) after 6 months of treatment, bicalutamide will be considered a feasible and promising therapy.

4.3 Intervention

Patients will receive bicalutamide at a dose of 150mg PO daily. Patients will be seen monthly for an assessment by a care provider familiar with the protocol. Clinical assessment and serum studies will be performed per protocol (See Time and Events Schedule, Section 10). Patients may be seen before their scheduled monthly follow-up if they are experiencing any adverse effects or symptoms that may be consistent with progression of disease. Patients will undergo a radiologic extent of disease evaluation (EOD) every 3 months. An EOD may be performed earlier than a 3 month interval if progression of disease is suspected. Response will be evaluated using RECIST criteria as complete response (CR), partial response (PR), stable disease (SD) or progressive disease (PD).

If a patient experiences unacceptable toxicity at the initial dose level, up to two dose reductions of 50mg each will be permitted. Dose reduction of bicalutamide from the initial dose of 150mg PO daily to100mg PO daily will occur for an individual patient if that patient experiences unacceptable toxicity. A second dose reduction of 50mg is acceptable. Toxicities will be graded using the NCI Common Terminology Criteria for Adverse Events (CTCAE) Version 3. Treatment may be delayed no more than 2 weeks to allow recovery from acute toxicity. In the event of a treatment delay exceeding 2 weeks, the patient will be withdrawn from the study.

[figure not shown]
A patient will be withdrawn from the study in the following situations:

- For an unacceptable toxicity, defined as a Grade 3 or 4 non-hematologic toxicity after 2 (50 mg) dose reductions (see Section 11.2.5); or
- For unacceptable toxicity that fails to resolve after a maximum treatment delay of 2 weeks; or
- Progression of disease

Treatment with bicalutamide will continue until one or more of the criteria for withdrawal from study are met. After 6 months of treatment, patients will be considered responders if they achieve a CR, PR or SD by RECIST criteria. At the investigator's discretion, and in the absence of disease progression by RECIST criteria, treatment with bicalutamide may continue beyond 6 months. Study drug is provided by AstraZeneca.

4.4 Correlative Studies

As a secondary objective, correlative studies will be performed to further elucidate the biology of this potentially novel subtype of ER(-)/PR(-)/AR(+) (ER(-) Class A) breast cancer and to measure the effect of androgen blockade on peripheral hormonal levels.

IRB#: 07-022A(13)

In patients with prostate cancer, the use of bicalutamide leads to increased testosterone and estrogen levels. Little data is available for women treated with androgen blockade, but changes in hormonal levels are anticipated. A serum hormone panel will be drawn at baseline, after one month and at the end of study. This serum hormonal panel will include: estradiol, total and free testosterone, and sex-hormone binding globulin.

Doane and colleagues describe a panel of IHC markers that identifies ER(-) class A breast cancers. A combination of ER, PR, SPDEF and ALCAM was estimated to predict ER(-)/PR(-) samples as ER(-) Class A with a sensitivity approaching 100% (95% CI 69 -100%) and a specificity of 94% (95% CI 79-99%)¹. Other genes that are overexpressed in ER(-) Class A will also be evaluated for their protein expression with IHC including Her2/neu and FGFR4. Her2/neu has been previously shown to stabilize AR protein levels and optimize binding of AR to promoters of androgen-regulated genes in prostate cancer cells¹⁴. FGFR4 is overexpressed in ER(-) Class A tumors, and previous research has demonstrated molecular 'cross-talk' between FGFR4 and Her2/neu leading to activation of the mTOR translational pathway and subsequent cyclin D1 activation¹⁵. This convergence of data suggests that further investigation into the role of FGFR4, Her2/neu and AR in ER(-) Class A breast cancers is warranted.

The ER(-) Class A subtype was noted by Doane and colleagues to be distinct from the 'basal subtype' previously identified by Perou and colleagues¹⁶. The basal subtype generally corresponds to a proportion of ER(-) breast cancers. Cytokeratins 5/6 and 17 are expressed in the basal subtype but not in the ER(-) Class A subtype. Correlative studies of CK 5/6 and 17 will be performed to further explore these previously noted differences in expression patterns between the ER(-) Class A and a basal subtypes.

Paraffin embedded tissue from primary tumor or metastatic sites which have tested AR+, will be requested from patients. Specimens will be collected, if available and at stored for the purpose of future correlative studies on the biology of AR+ breast cancer (ie, creation of tissue microarray of ER(-)/PR(-)/AR(+) breast cancer).

Based on the preclinical data demonstrating a response to androgen blockade in a subset of ER(-) /PR(-)/AR(+) breast cancer, further study of androgen blockade is warranted. A feasibility study to evaluate the efficacy of bicalutamide in women with ER(-)/PR(-)/AR(+) breast cancer is therefore rational, and a logical next step. This is an important study for the field of breast cancer research because bicalutamide may allow a greater number of patients with breast cancer the option of treatment with hormonal therapy instead of, or in addition to, chemotherapy.

[figure not shown]

5.1 THERAPEUTIC/DIAGNOSTIC AGENTS

CASODEX® (bicalutamide)

Drug Composition:

CASODEX® (bicalutamide) Tablets for oral administration contain 50 mg of bicalutamide, a non-steroidal antiandrogen with no other known endocrine activity. The chemical name is propanamide, N-[4-cyano-3-(trifluoromethyl)phenyl]-3-[(4-fluorophenyl)sulfonyl]-2-hydroxy-2-methyl-,(+-). The structural and empirical formulas are:

Bicalutamide has a molecular weight of 430.37. The pKa' is approximately 12. Bicalutamide is a fine white to off-white powder which is practically insoluble in water at 37°C (5 mg per 1000 mL), slightly soluble in chloroform and absolute ethanol, sparingly soluble in methanol, and soluble in acetone and tetrahydrofuran.

CASODEX is a racemate with its antiandrogenic activity being almost exclusively exhibited by the R-enantiomer of bicalutamide; the S-enantiomer is essentially inactive.

The inactive ingredients of CASODEX Tablets are lactose, magnesium stearate, methylhydroxypropylcellulose, polyethylene glycol, polyvidone, sodium starch glycollate, and titanium dioxide.

Drug is supplied as 50 mg Tablets by AstraZeneca:

(NDC 0310-0705) White, film-coated tablets (identified on one side with "CDX50" and on the reverse with the "CASODEX logo") are supplied in unit dose blisters of 30 tablets per carton (0310-0705-39), bottles of 30 tablets (0310-0705-30) and bottles of 100 tablets (0310-0705-10).

Store at controlled room temperature, 20°-25°C (68°-77°F).

IRB#: 07-022A(13)

Pharmacokinetics:

Bicalutamide has good oral absorption (though the absolute oral bioavailability is not known). Taking the drug with food has no significant effect on absorption. Both the parent drug and its metabolites have renal and hepatic clearance. Renal impairment has no significant effect on clearance. Patients with severe hepatic disease have increased plasma half-life of a metabolite of bicalutamide. *In-vitro* protein binding studies have shown that bicalutamide can displace coumarin anticoagulants from binding sites. Patients already on coumarin anticoagulants should have closely monitored Prothrombin times while taking bicalutamide. In men, the mean half-life of the drug is 5.8 days (standard deviation 2.29).

Contraindications:

Bicalutamide is contraindicated in any patient who has shown a hypersensitivity reaction to the drug or any of the tablet's components. It is contraindicated for use in pregnant women.

Toxicity:

Bicalutamide has not been tested in women at the intended doses for this study. Toxicities that have been reported in men with prostate cancer are listed above, in section 3.1 (with further details in Appendix A).

The anticipated toxicities of bicalutamide in women at doses of 50 - 150 mg include (listed in order of most likely to least likely to occur):

[figure not shown]
- Breast pain/tenderness
- Hot flashes
- Diarrhea
- Abnormal Hepatic Function
- Anemia
- Constipation
- Nausea
- Abdominal pain

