6.1 CRITERIA FOR SUBJECT ELIGIBILITY

6.2 Subject Inclusion Criteria

A patient will be eligible for androgen receptor expression testing if the following criteria are met:

- Pathologically confirmed adenocarcinoma of the breast which is ER(-) and PR(-).
- Non-measurable or Measurable, metastatic disease

IRB#: 07-022A(13)

A patient will be eligible for participation in the therapeutic trial if the following criteria are met:

- Androgen receptor expression testing confirms that the patient's tumor is ER(-)/PR(-) /AR(+). ER, PR and AR are considered positive if greater than 10% of cell nuclei are immunoreactive. Receptor testing may be performed on either primary tumor specimen or tissue from a metastatic site.
- Prior neo-adjuvant or adjuvant chemotherapy is allowed. Any number of chemotherapy regimens are allowed for metastatic disease. There is no restriction on prior treatment with hormonal agents.
- Prior treatment with trastuzumab must have been given if patient has Her2/neu positive disease (defined as IHC=3+ or FISH amplified).
- At least 2 weeks since prior cytotoxic chemotherapy. Patients should have recovered from all acute effects of such therapy.
- Absence of active brain metastatic disease or leptomeningeal disease. If patient has a history of brain metastases, lesions must be stable for at least 3 months (as documented by either head CT or brain MRI).
- At least 4 weeks from major surgery with full recovery
- ECOG performance status 0-1
- Age 18 years or greater
- Laboratory parameters as follows:
 - \circ ANC $\geq 1.5 \times 10^9$ cells/L
 - \circ Platelets $\geq 100 \text{ x } 10^9 \text{ cells/L}$
 - $\circ \quad Hgb \geq 9g/dL$
 - AST (SGOT), ALT (SGPT) ≤ 2.5 x upper limit of normal range (ULN); total bilirubin ≤ 1.5 x ULN; alkaline phosphatase ≤ 2.5 x ULN (unless bone metastases are present in the absence of liver metastases), creatinine ≤ 1.5 mg/dL
- If female of childbearing potential, pregnancy test is negative
- If fertile, the patient agrees to use an effective method to avoid pregnancy for the duration of the study
- Informed consent has been obtained

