8.1 PRETREATMENT EVALUATION

Baseline evaluations will be performed for ER(-)/PR(-)/AR(+) patients to determine study eligibility. Patients who have received any chemotherapy must have a washout period of 2 weeks before the first dose of study drug is administered. The investigator will document the designated washout period in the patient's source documentation.

The following must be completed within 28 days of initiation of study drug:

[figure not shown]
- Medical history including history of prior therapy
- Medication list (include medications taken within 30 days of baseline visit)
- Physical exam, height and weight.
- Vital signs
- ECOG performance status.
- CBC with differential and platelet count, comprehensive blood panel (including chemistries and liver function tests), tumor markers (Ca15-3 & CEA, or CA 27.29)
- Estradiol, total testosterone, free testosterone, sex-hormone binding globulin,
- Serum pregnancy test (for women of childbearing-potential) will be conducted within 72h of first study drug administration (negative results required for study drug administration).
- CT scan of chest, abdomen and pelvis
- Bone scan or PET scan

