9.1 TREATMENT/INTERVENTION PLAN

9.2 Agent Administration

Treatment will be administered on an outpatient basis. Bicalutamide is administered orally at 150 mg (three 50mg tablets) on a continuous daily schedule. A cycle length consists of 4 weeks of therapy. Please refer to the Time and Events Calendar (Section 10) for a detailed description of required tests. Radiographic tumor assessment will take place every 3 cycles.

Expected adverse events for bicalutamide are described in Section 5.0. Appropriate dose modifications for bicalutamide are described in Section 4.2 and Section 11.2. Two 50mg dose reductions are permitted per protocol. A treatment delay of up to 2 weeks is permitted. Therapy will continue until disease progression or unacceptable toxicity.

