10.0 EVALUATION DURING TREATMENT/INTERVENTION

Day 0 and every 4 weeks (+/- 5 days), the following clinical and laboratory assessments must be done prior to continuation of treatment with bicalutamide:

- History and physical examination, including:
 - Vital signs
 - ECOG performance status
 - o Weight
 - Concomitant medications
- Laboratory assessments, including: (screening labs can be used as Day 0 labs)
 - CBC with differential and platelet count
 - Comprehensive metabolic panel (Na, K, Cl, CO2, BUN, Creatinine, Ca, Glucose, Total Protein, Albumin, Alkaline Phosphatase, Total Bilirubin, AST and ALT)
- Adverse Event Evaluation (toxicity assessment using the NCI CTC version 3)
- Blood for correlative study of hormonal levels including estradiol, total testosterone, free testosterone, and sex-hormone binding globulin will be performed at baseline, after Cycle #1 and at the end of study. (See further description below)

Every 12 weeks (+/- two weeks), tumor assessments will be performed. Patients with measurable disease will be evaluated for complete response (CR), partial response (PR), stable disease (SD) or progressive disease (PD) using RECIST criteria, using the same modality of imaging performed at baseline. Patients with non-measurable disease will be evaluated for either stable disease or progressive disease. Responders and stable disease patients will continue on study unless they develop unacceptable toxicity. Progressive disease or unacceptable toxicity (after a maximum of two dose reductions) will be the criteria for treatment failure and discontinuation from the study.

Response assessment will include:

- Radiologic scans of disease sites (e.g. CT scan of chest, abdomen and pelvis and PET or bone scan if there are bone lesions identified on pre-study bone imaging)
- Measurement of all target lesions that are followed by physical examination
- Patients achieving a CR or PR must have confirmation of response at least 4 weeks following the initial response determination.
- End-of-Study (EOS) Evaluation: At the time patients are removed from study, laboratory and clinical evaluations to assess adverse events (AEs) will be performed. Serum hormone panel including estradiol, free and total testosterone and serum hormone binding globulin will be collected. Radiologic studies for antitumor response will be repeated if they have not been performed within the previous 28 days.

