^b after study consent form has been signed, pathological testing of tumor for androgen receptor (AR) status will be performed. If patient's tumor is AR+ then they will be eligible to participate in the therapeutic study. If AR- they will not be permitted to participate in study.

- ^c body weight only
- ^d by physical exam
- ^e confirm response 28 days
- ^f females of childbearing potential only, within 72 hours of drug initiation

^g bone scan or PET must be repeated if bone disease is known from baseline scans. If patient does not have bone disease, follow-up bone or PET scans are at the discretion of the treating physician. If PET/CT scans are being performed and can monitor for bone lesions, then no further bone scans are necessary.

* after Cycle 1

^h Comprehensive blood panel may include the following: Na, K, Cl, CO2, BUN, Creatinine, Ca, Glucose, Total Protein, Albumin, Alkaline Phosphatase, Total Bilirubin, AST and ALT

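### Pregnancy is tested for once, within 72 hours of the first dose, and not again during open-ended bicalutamide dosing, although the drug is contraindicated in pregnancy

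*Combined protocol and SAP*

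**What the plan says.** On the hazard, Section 5.1 (Contraindications) states: "It is contraindicated for use in pregnant women". The label in Appendix A places the drug in Category X and advises against use in women who are or may become pregnant.

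On testing, Section 8.1 reads "Serum pregnancy test (for women of childbearing-potential) will be conducted within" 72 hours of the first dose, and a negative result is needed before dosing. In the Time and Events Schedule (Section 10.0) the pregnancy-test row has one mark, in the pre-study column. Footnote f defines it as "females of childbearing potential only, within 72 hours of drug initiation".

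On treatment, Section 10.0 sets out a four-weekly list under the words "the following clinical and laboratory assessments must be done prior to continuation of treatment with bicalutamide". It covers history, examination, blood count, metabolic panel and adverse-event review, with a hormone panel at set times. It contains no pregnancy test. For the end of study the section says "At the time patients are removed from study, laboratory and clinical evaluations to assess adverse events (AEs) will be performed", adds the hormone panel and imaging, and again names no pregnancy test.

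On duration, Section 9.2 says "Therapy will continue until disease progression or unacceptable toxicity", and Section 4.3 allows dosing past six months.

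On prevention, Section 6.2 requires: "If fertile, the patient agrees to use an effective method to avoid pregnancy for the duration of the study".

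**The concern.** The protocol requires proof that a woman is not pregnant before the first tablet, then never checks again during dosing that may last many months. Eligibility sets a minimum age of 18 and no menopausal restriction, so women of childbearing potential are expected in the trial. A contraception agreement lowers the chance of pregnancy but cannot show when it has failed. A site that followed the schedule exactly could keep dosing a symptom-free pregnancy, even though it draws blood every four weeks.

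The stake is fetal harm. Appendix A reports hypospadias and reduced anogenital distance in male rat offspring from 10 mg/kg/day, about two thirds of human therapeutic concentrations at a 50 mg dose. This trial starts at 150 mg. Sample size, error rates and the primary analysis are not affected.

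**Working it through.** The plan gives no figure on this point, so there is none to reproduce. The check has three parts.

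**1. Is a repeat test scheduled anywhere in the protocol body?** Sections 6.2 and 8.1 both concern entry. The schedule row has one mark, and its footnote ties that mark to drug initiation, so it cannot stand for an on-treatment test. The four-weekly and end-of-study lists in Section 10.0 name none. The places agree: one test, none later.

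**2. How many dosing cycles go untested, and how many pregnancies might occur?**

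Inputs from the documents: 28 patients; four-week cycles; scans every 12 weeks; six-month rates of 5% (unacceptable) and 20% (promising) from Section 14.0.

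Assumptions not in the documents: everyone reaches week 12; those who do not stay to six months leave then; 10% to 50% of patients are of childbearing potential; contraception fails at 1% to 10% per woman-year.

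- Visits without a test through week 24, at 5% staying: 28 × 3 + (28 × 0.05) × 3 = 88.2.
- At 20% staying: 28 × 3 + (28 × 0.20) × 3 = 100.8.
- Visits in women at risk: 88.2 × 0.10 = 8.8 (low) to 100.8 × 0.50 = 50.4 (high).
- Woman-years, counting 28 days per visit: 8.82 × 28 / 365.25 = 0.68 to 50.4 × 28 / 365.25 = 3.86.
- Expected pregnancies: 0.68 × 0.01 = 0.007 to 3.86 × 0.10 = 0.39.

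Exits before week 12 would lower these figures. Dosing after week 24 raises them, by 365 / 28 = about 13 further untested visits per patient per year.

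**3. What would per-cycle testing need?** Low: 10% of 28 is about 3 women, and 3 × 3 visits = 9 assays. High: 50% of 28 is 14 women, and 14 × 6 visits = 84 assays, or 14 × 7 = 98 with a separate end-of-study test. The visits and blood draws already exist.

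**The case against.** The strongest reply is that the protocol already does a good deal. It requires a serum test, a negative result and contraception. At day 28 it already has a history, an examination and an adverse-event review. Section 11.1 asks investigators to look promptly for the cause of every adverse event, so breast tenderness or nausea in a woman of childbearing potential should start a work-up. For imaging, "Every 12 weeks (+/- two weeks), tumor assessments will be performed", and Section 10.0 gives chest, abdomen and pelvis CT as its example. The supplied label sets interval monitoring for transaminases but none for pregnancy, so a four-week interval is a choice and not a rule breached.

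Most of this stands, and it limits the point in four ways.

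- A reader might infer that per-cycle testing finds a pregnancy 56 days sooner, since the first test would fall on day 28 (23 to 33) and the first scan on day 84 (70 to 98), and 84 − 28 = 56. That is a gap between two calendar dates, not a reduction in exposure. It ignores the date of conception and the clinical review already held on day 28.
- A reader might infer that scans usually miss the pelvis. The wording on disease sites makes that possible, but it is not the default.
- A reader might put the upper figure at 0.64 pregnancies (28 × 6 × 0.50 × 28 / 365.25 × 0.10). That needs all 28 patients on drug at week 24, well above the 20% the design calls promising.
- An end-of-study test cannot prevent dosing, which has already stopped.

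What the reply does not meet is the symptom-free early pregnancy. Work-up depends on symptoms, some of which are expected from the drug (breast tenderness, nausea, abdominal pain), and scans are 12 weeks apart and aimed at tumour.

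**Conclusion.** The gap is real and concerns detection. The protocol body has no scheduled test that would find a pregnancy starting after the first dose. About 0.007 to 0.4 pregnancies are expected through week 24 under the stated assumptions. Neither the childbearing share nor the failure rate comes from the documents, so this is a range and not an estimate. The recommendation rests on the severity of the hazard and the low cost of an assay, not on numbers. It is a change the sponsor should make; it does not bear on the validity of the trial's result.

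A reader might infer that a site would have no basis to stop or report a pregnancy. The documents do not support that. Section 5.1 bars dosing a known pregnancy, Section 13.0 has intercurrent-illness and investigator-discretion clauses, and Section 11.2.2 counts important medical events and congenital abnormalities as serious. Nor can anything be concluded from the consent form, which is not in the public document and may ask patients to report a suspected pregnancy. Such an instruction would still not be a scheduled test.

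**What to change.** For women of childbearing potential, extend the pregnancy-test row of the Time and Events Schedule, and the four-weekly list in Section 10.0, to every four-week cycle. Run the test on blood already drawn and require a negative result before bicalutamide continues. An end-of-study test is optional; its only use is to identify an exposed pregnancy for follow-up. Naming pregnancy in Section 13.0 as a reason to stop, and in Sections 11 and 17 as reportable with outcome follow-up, would be a helpful clarification and no more.

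The laboratory cost is the 9 to 98 assays worked out above, with no new visits. The larger cost is the amendment. It needs approval by the coordinating centre's IRB and then by each site's IRB, for which Section 16.2.1 allows 90 calendar days. If the amendment is classed as safety-related, the same section stops new enrolment at each participating site until that site's IRB has approved.
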